# **10** Adverse Events and Device Deficiencies

### 10.1 Definitions

### 10.1.1 Adverse Event

An adverse event (AE) is any untoward medical occurrence, unintended disease or injury, or untoward clinical signs (including abnormal laboratory findings) in subjects, users or other persons whether or not related to the medical device or the procedures required for implant or use, and whether anticipated or unanticipated.

NOTE 1: This definition includes events related to the medical device or the comparator device.

NOTE 2: This definition includes events related to the procedures involved.

NOTE 3: For users and other persons, this definition is restricted to events related to the use of medical devices.

### **10.1.2** Adverse Device Effect

An adverse device effect (ADE) is an AE related to the use of a medical device.

NOTE 1: This includes any AE resulting from insufficiencies or inadequacies in the instructions for use, the deployment, the implantation, the installation, the operation, or any malfunction of the medical device.

NOTE 2: This definition includes any event resulting from use error or from intentional misuse of the medical device.

NOTE 3: This includes 'comparator' if the comparator is a medical device.

### **10.1.3** Serious Adverse Event

A serious adverse event (SAE) is any AE that led to any of the following:

1) death,

- 2) serious deterioration in the health of the subject, users, or other persons as defined by one or more of the following:
- a life-threatening illness or injury, or

- a permanent impairment of, or damage to, a body structure or a body function including chronic diseases, or
- in-patient hospitalisation or prolonged hospitalisation, or
- medical or surgical intervention to prevent life-threatening illness or injury or permanent impairment or damage to a body structure or a body function,
- 3) foetal distress, foetal death or a congenital physical or mental abnormality, or birth defect including physical or mental impairment.

NOTE: Planned hospitalisation for a pre-existing condition, or a procedure required by the CIP, without serious deterioration in health, is not considered a SAE.

### 10.1.4 Serious Adverse Device Effect

A serious adverse device effect (SADE) is an ADE that has resulted in any of the consequences characteristic of a SAE.

### 10.1.5 Unanticipated Serious Adverse Device Effect

An unanticipated serious adverse device effect (USADE) is a SADE, which by its nature, incidence, severity, or outcome has not been identified in the current version of the IB and IFU.

A USADE is also known as a UADE (Unanticipated Adverse Device Effect) for the purposes of US FDA reporting.

NOTE: An anticipated serious adverse device effect is an effect, which by its nature, incidence, severity, or outcome has been identified in the IB and IFU.

### **10.1.6 Adverse Events of Special Interest**

There are no adverse events of special interest for this clinical investigation.

### **10.1.7** Device Deficiency

A Device Deficiency (DD) is an inadequacy of a medical device with respect to its identity, quality, durability, reliability, usability, safety, or performance.

NOTE 1: Device Deficiencies include malfunctions, use errors, and inadequacy in the information supplied by the manufacturer including labelling.

NOTE 2: This definition includes device deficiencies related to the IMD or the comparator.

### **10.1.8** Serious Health Threat

A signal from any adverse event or device deficiency that indicates an imminent risk of death or a serious deterioration in the health in subjects, users or other persons, and that requires prompt remedial action for other subjects, users or other persons.

NOTE: This would include events that are of significant and unexpected nature such that they become alarming as a potential serious health hazard or possibility of multiple deaths occurring at short intervals.

## 10.2 Recording and Handling of Adverse Events

Subjects shall be carefully monitored during the clinical investigation and the investigator should enquire about AEs at investigation visits.

All AEs will be recorded from the time of implantation. AE recording will continue for each subject until completion of their End of Study visit. Ongoing SAEs and SADEs will be followed for an additional 30 days, or until resolution or stabilization of the event, whichever comes first. Management of the SAE/SADE beyond clinical investigation completion will be absorbed into standard clinical and medical care by the participating clinical investigational site.

Source notes should indicate the evaluation for AEs, even if there was none to report. All required AEs will be reported if observed, even if anticipated and/or acknowledged as a risk factor in the consent.

All AEs will have the following information documented: start and stop dates, action taken, outcome, severity and investigators opinion on the potential relationship to the Osia 2 system and study procedures. If an AE changes in severity, the most severe (highest) grade will be captured for that event on the Adverse Events CRF.

### 10.2.1 Assessment of Severity

The Principal Investigator (or qualified delegate) will make an assessment of severity for each event based on clinical judgement. The intensity of each event recorded in the CRF should be assigned to one of the following categories:

Mild	An event that is easily tolerated by the subject, causing minimal discomfort and not interfering with everyday activities.	
Moderate	An event that is sufficiently discomforting to interfere with normal activities	
Severe	An event which is incapacitating and prevents normal everyday activities	

### 10.2.2 Assessment of Causality

The Investigator will assess the potential causal relationship of each event, using clinical judgement. Alternative causes, such as natural history of underlying diseases, other risk factors and the temporal relationship of the event to the Osia 2 system will be considered and investigated. The causal relationship to the Osia 2 system is to be assessed by the Investigator (or medically qualified delegate) and should be assessed using the following classifications:

Not related	
 
Relationship to the medical device or procedures can be excluded when:
 
the event is not a known side effect of the product category the device belongs to or of similar devices and procedures;
 

	• the event has no temporal relationship with the use of the device or the procedures;
	• the event does not follow a known response pattern to the medical device (if the response pattern is previously known) and is biologically implausible;

### CIP | VV-TMF-02337 | 5.0 Approval Date (GMT+0): 06 Nov 2023

	
 
the discontinuation of medical device application or the reduction of the level of activation/exposure - when clinically feasible - and reintroduction of its use (or increase of the level of activation/exposure), do not impact on the event;
 

	
 
the event involves a body-site or an organ not expected to be affected by the device or procedure;
 

	
 
the event can be attributed to another cause (for example, an underlying or concurrent illness/ clinical condition, an effect of another device, drug, treatment or other risk factors);
 

	
 
the event does not depend on a false result given by the investigational medical device used for diagnosis, when applicable;
 

	
 
harms to the subject are not clearly due to use error;
 

	In order to establish the non-relatedness, not all the criteria listed above might be met at the same time, depending on the type of device/procedures and the event.
Unlikely related	The relationship with the use of the medical device seems not relevant and/or the event can be reasonably explained by another cause, but additional information may be obtained.
Possibly related	The relationship with the use of the medical device is weak but cannot be ruled out completely. Alternative causes are also possible (for example, an underlying or concurrent illness/ clinical condition or/and an effect of another device, drug or treatment). Cases where relatedness cannot be assessed or no information has been obtained should also be classified as possibly related.
Probably related	The relationship with the use of the medical device seems relevant and/or the event cannot be reasonably explained by another cause, but additional information may be obtained.
Definitely related	The event is associated with the medical device or with procedures beyond reasonable doubt when:
	
 
the event is a known side effect of the product category the device belongs to or of similar devices and procedures;
 

	
 
the event has a temporal relationship with the medical device use/application or procedures;
 

	
 
the event involves a body-site or organ that
 

	
 
the medical device or procedures are applied to
 

	
 
the medical device or procedures have an effect on;
 

	
 
the event follows a known response pattern to the medical device (if the response pattern is previously known);
 

	
 
the discontinuation of medical device application (or reduction of the level of activation/exposure) and reintroduction of its use (or increase of the level of activation/exposure), impact on the event (when clinically feasible);
 

	
 
other possible causes (for example, an underlying or concurrent illness/ clinical condition or/and an effect of another device, drug or treatment) have been adequately ruled out;
 

	
 
harm to the subject is due to error in use;
 

	
 
the event depends on a false result given by the medical device used for diagnosis, when applicable;
 

	In order to establish the relatedness, not all the criteria listed above might be met at the same time, depending on the type of device/procedures and the event.

### 10.2.3 Assessment of Seriousness

The Investigator will assess the seriousness of each event according to clinical judgement and the definition provided in section 10.1.3.

### 10.2.4 Assessment of Expectedness

An event should be considered unanticipated if the nature, severity, or frequency of that event is not consistent with the applicable safety reference information, such as the hazards analysis, IB, or Product Information/IFU if the product is approved for marketing.

For this clinical investigation the listed items in Section 7.2 and 7.3 of this CIP and/or the instructions for use (IFU) cleared for the Osia 2 system are anticipated ADEs.

Anticipated	An adverse device effect (ADE) which by its nature, incidence, severity, or outcome is consistent with the applicable safety reference information (for example, IB, IFU).
Unanticipated	An adverse device effect (ADE) which by its nature, incidence, severity, or outcome is not consistent with, or has not been identified in the applicable safety reference information (for example, IB, IFU).

#### 10.2.5 Non-reportable Adverse Events

Any adverse events (AEs) that are experienced by study subjects prior to implantation will not be recorded or reported.

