### CIP | VV-TMF-02337 | 5.0 Approval Date (GMT+0): 06 Nov 2023

Visit Type	Screening Baseline Surge	Surgery	ery Visit 1	Visit 2	Visit 3	Visit 4	Visit 5	
Timing of Investigation	Day -60	Day -60	Day -0	Week 2	Week 4	Month 3	Month 6	Month 12
Visit window (±) (calendar days)	NA	NA	NA	±7Day	± 7 days	± 14 days	± 14 days	± 14 days
Surgical questionnaire (including skin thickness)			X					
Aided soundfield thresholds – ear to be implanted (pre-op) OR treated ear (post-op)		Xª			Xp	Хр	Xp	
Aided speech perception testing in quiet – ear to be implanted (pre-op) OR treated ear (post-op) – CNC words 60dBA		Xa				Xp	Xp	
Aided speech perception testing in noise – ear to be implanted (pre-op) OR treated ear (post-op) – BKB-SIN 65dBA		Xa				Xp	Xp	
Parental questionnaire – SSQ Parent		X				x	X	
Device exposure			X	X*	x	X*	X*	X
Device programming – as needed		X			х	х	х	
Device Use Questionnaire (including hours of use)						x	x	
Concomitant medications		X	x	x	x	x	X	X
Adverse Events			x	x	x	x	x	x

<sup>a Baseline aided testing performed with Baha 5 Power device on a softband.

<sup>b Postoperative aided testing performed using the Osia 2 Sound Processor.

\* Device exposure form only completed at this visit if needed.

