### 6.3.3 Safety Evaluations and Procedures

Safety data will be reviewed in accordance with the Sponsor's standard operating procedures regarding safety events. The risks and anticipated ADEs for the Osia 2 system, as identified in Sections 7.2 and 7.3 below, will be assessed in the clinical investigation via reporting of all AEs/ADEs from the time of subject implantation until subject last visit. Ongoing SAEs and SADEs will be followed for an additional 30 days, or until resolution or stabilization within the 30-day period following End of Study. Management of the SAE/SADE beyond clinical investigation completion will be absorbed into standard clinical and medical care by the participating clinical investigational site.

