### 6.3.4.10 Collected from Surgery

- Adverse Events: Includes initial report and review of ongoing adverse events. Adverse events should be reviewed at each visit.
- Device Exposure
- Device Deficiencies

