## 7.3 Risks Associated with Participation in the Clinical Investigation

In addition to the anticipated surgical and adverse device effects of the Osia 2 System, the following risks may also present when participating in the clinical investigation:

- Exposure to sounds produced in the test battery that could be perceived as too loud
- Testing procedures that may produce anxiety or fatigue
- Discomfort and potential abrasion to the ear canal due to placement of insert earphones
- Discomfort associated with the fitting of the Baha 5 Power on the softband
- Possible interactions with concomitant medications and residual risks for the device are not anticipated in this clinical investigation.

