### 8.2 Endpoints

### 8.2.1 Primary Endpoint

The primary endpoint is adverse events and serious adverse events Surgery through Visit 4 (6 Months). Events will be summarized by type, frequency, and severity.

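### AE recording starts at implantation, so one risk the protocol promises to assess by AE reporting can never be recorded, and the primary safety window has two start points

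*Protocol*

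**What the plan says.** Two sections of the Protocol set the start of AE recording. Section 10.2 says "All AEs will be recorded from the time of implantation", and section 10.2.5 adds "Any adverse events (AEs) that are experienced by study subjects prior to implantation will not be recorded or reported". Neither makes an exception for serious events or for events caused by study procedures.

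Section 6.3.3 covers the risks of both section 7.2 and section 7.3, saying that they "will be assessed in the clinical investigation via reporting of all AEs/ADEs from the time of subject implantation until subject last visit". Section 7.3 is the list of risks from taking part in the study, and one of its items is "Discomfort associated with the fitting of the Baha 5 Power on the softband". Footnote a to the Schedule of Events places that device in time: "Baseline aided testing performed with Baha 5 Power device on a softband". Footnote b says that aided testing after surgery uses the Osia 2 Sound Processor.

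Other parts of the Protocol start from Surgery. AEs appear under the heading "Collected from Surgery" (6.3.4.10). The AE row of the Schedule of Events has its first mark in the Surgery column. Section 6.1.1 gathers safety events for Surgery and Visits 1 to 5. Section 8.2.1 runs the primary endpoint from Surgery to Visit 4 at 6 months, and SAP 5.6.1 uses the same window.

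**The concern.** Safety is the primary objective, and the primary endpoint is a description of adverse events with no hypothesis test. Its value depends on what sites are told to record and from when.

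The recording rule shuts out a period in which enrolled children aged 5 to 11 undergo study-specific testing, yet the protocol says the risks of that testing will be assessed by AE reporting. An empty row for such a risk would show only that nobody was allowed to write the event down.

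The day of surgery raises a second problem. If sites differ on whether implantation means the operation or the moment the implant is placed, they will differ on which intraoperative events enter the primary endpoint.

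**Working it through.** **1. The plan's own figure.** Protocol 8.4 and SAP 4 give n = 50 and a greater than 95% chance of seeing at least one event at a population rate of 5.9%. The formula is 1 − (1 − p)^n. With the numbers in, 1 − (1 − 0.059)^50 = 0.9522, so the figure reproduces. A rate of 1 − 0.05^(1/50) = 5.82% gives exactly 95%.

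**2. What that figure presumes.** It holds only for events inside the recording window. If a share c of events falls inside the window, the chance of at least one recorded event is 1 − (1 − c·p)^50. For an event that arises only before implantation, c = 0 and the result is 0 at every p. The documents give no pre-implant event rate, so the rates below are assumptions; 5.9% is the plan's own example.

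| Assumed rate | At least one event if recorded (c = 1) | Under 10.2.5 (c = 0) |
|---|---|---|
| 1% | 39.5% | 0 |
| 2% | 63.6% | 0 |
| 5% | 92.3% | 0 |
| 5.9% | 95.2% | 0 |
| 10% | 99.5% | 0 |

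**3. Which 7.3 risks are affected.**

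| Risk in 7.3 | When it can arise | Captured? |
|---|---|---|
| Softband fitting discomfort | Baseline only (footnote a; 6.3.4.2) | Never |
| Loud test sounds | Screening and Baseline; testing at Visits 2 to 4 | Only if it occurs after surgery |
| Anxiety or fatigue from testing | Same | Only if it occurs after surgery |
| Ear-canal discomfort or abrasion from insert earphones | Screening and Baseline; after surgery only if insert earphones are used, for example for masking at Visit 2 (the protocol does not say) | Only if it occurs after surgery |

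Section 10.2.4 classes the items in 7.2 and 7.3 as anticipated ADEs. The first row is therefore an anticipated ADE that the plan bars from capture.

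**4. Other recording routes.** Section 6.3.4.9 collects only concomitant medications and protocol deviations from Baseline. Section 10.1.1 counts procedure-related events as AEs, and section 10.4.1 requires every AE that meets the SAE criteria to go to the sponsor. Section 10.2.5 excludes pre-implant events from both without saying how the sections fit together.

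**5. The start point on the day of surgery.**

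| Starts at Surgery | Starts at implantation |
|---|---|
| Schedule of Events, AE row | 6.3.3 |
| 6.1.1 | 10.2 |
| 6.3.4.10 | 10.2.5 |
| 8.2.1; SAP 5.6.1 | |

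Section 7.2.1 lists anaesthetic risks, and 7.2.2 lists CSF leakage and subdural injury. Any of these can precede placement of the implant. Under the left column such an event counts in the primary endpoint. Under a literal reading of the right column it is not recorded.

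**The case against.** The strongest reply is that the rule is deliberate. The change history shows the section on non-reportable events was added in version 4. The primary objective is the safety of the Osia 2 System, which an event at preoperative audiometry cannot inform. The 7.3 risks are mostly minor. This supports keeping pre-surgery events out of the primary endpoint. It does not support leaving them unrecorded while 6.3.3 promises to assess them, and none of the general rationales given for version 4 explains the conflict.

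Four stronger readings are tempting, and the documents do not support them.

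- A reader might infer that anaesthetic or drilling events are excluded from the primary endpoint. Four places in the Protocol collect AEs from Surgery, and 6.3.4.1 and 6.3.4.2 use implantation loosely for the date of surgery. This is a contradiction to reconcile, not a settled exclusion.
- A reader might infer that none of the 7.3 risks can be recorded. That is shown only for softband discomfort.
- A reader might infer 60 days of unmonitored procedures. The 60 days are the window within which Screening and Baseline testing must fall, not a period of continuous exposure.
- A reader might infer that pre-surgery harm is invisible to everyone. An AE that leads to withdrawal is documented as the reason if the family gives it (6.2.6), and investigators report safety events to their ethics committee under local regulations (10.4.1). These routes are partial and do not replace an AE record that the sponsor and the IDMC can review.

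**Conclusion.** The point holds as a conflict within the Protocol. The recording rule in 10.2 and 10.2.5 cannot deliver the assessment promised in 6.3.3. For softband discomfort the probability of capture is exactly zero; for the other test-related risks in 7.3, capture is partial. The primary endpoint also lacks a single start point on the day of surgery, and the number of operative events this could move in or out cannot be worked out from the documents.

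The effect on the device-safety conclusion is probably small, because the listed Baseline risks are discomfort, anxiety or fatigue, loudness and possible ear-canal abrasion. The correction is still worth making: the subjects are children, safety is the primary objective, and 10.2.5 as written excludes even a serious pre-surgery event.

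This rests on two assumptions: that the Baha 5 Power softband is fitted for the study only at Baseline, as the Schedule of Events and 6.3.4.2 indicate, and that sites follow 10.2.5 as written. A child in whom implantation fails falls outside the analysis population in Protocol 8.5 and SAP 5.2 whichever start point is chosen; that is a separate matter.

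**What to change.** - In 6.3.3, 10.2 and 10.2.5, record AEs and SAEs from the first study-specific procedure after consent. Bring 6.3.4.10 and the AE row of the Schedule of Events into line.
- Tabulate events before surgery separately, as pre-surgery events, outside the primary endpoint.
- Give the primary window one start that covers the whole surgical procedure, including anaesthesia, consistent with Surgery in 8.2.1. Use that term throughout the Protocol and the SAP.
- As a separate clerical correction, reconcile the Device Deficiencies row of the Schedule of Events, which first has a mark at Visit 1, with 6.3.4.10, which collects deficiencies from Surgery.

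The cost is a wording amendment, an AE form opened no later than Baseline that also takes events from Screening tests, one added table, and a few extra minor events. The primary endpoint's content and its 6-month end point do not change.

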### 10.3 Recording and Handling of Device Deficiencies

Subjects shall be carefully monitored during the clinical investigation and routinely questioned about DDs at investigation visits. Source notes should indicate the evaluation for DDs, even if there are none to report.

The Investigator shall assess if the DD led to an AE or could have led to a serious medical occurrence (serious adverse device effect) if;

- 1) suitable action had not been taken,
- 2) intervention had not been made, or,
- 3) circumstances had been less fortunate

All DDs will be documented in the source notes and the DD page of the CRF. As the study device is a commercially cleared product, the standard commercial returns process applies.

### **10.4 Reporting Responsibilities**

The Investigator is responsible for reporting all AEs and DDs in the CRF.

### 10.4.1 Investigator Reporting of Serious Adverse Events

All AEs meeting the criteria for an SAE, or DD that could have led to an SADE must be reported to the Sponsor in a timely manner. Reporting is achieved through completion of the events details in the Adverse Event page of the eCRF.

The Investigator shall always provide an assessment of causality at the time of the initial report, as described in section 10.2.2 'Assessment of Causality'. If data obtained after reporting indicates that the assessment of causality is incorrect, then the SAE form may be appropriately amended, signed, dated, and resubmitted to the Sponsor.

If the Investigator does not have all other information regarding an SAE, he/she will not wait to receive additional information before reporting the event. The reporting forms shall be updated when additional information is received.

The Investigator is responsible for reporting of safety events to their local EC using the applicable report form, in accordance with local regulations.

